3.4.3.3. Electrocardiogram

Descriptive statistics for ECG parameters (heart rate, PR interval, QRS interval, QT interval, and QTcF) and changes from baseline values at each assessment time point to the end of study will be presented by treatment group. The QTcF will be calculated using the Fridericia correction.

All recorded values for the standard 12 lead electrocardiogram parameters will be presented in a by-subject listing.

Categorical Analyses

The number and percentage of subjects with absolute ECG values and change from baseline in the ranges shown in Table 6 will be presented in Electrocardiogram Categorical Summary by Visit and Time Point.

Subjects without a postbaseline measurement for a given treatment period will be excluded from the summary statistics (e.g., denominator of the summary statistic) for that time point.

In addition, in the same summary, QTcF will also be summarized by the following categories, Normal (males < 430 , females ≤ 450), Borderline (males $> 430, \leq 450$); females $> 450, \leq 470$) and Prolonged (males > 450 , females > 470).

Individual ECG data collected during the study will be presented in a listing. A separate listing of subjects with values of QTcF > 500 msec or an increase > 60 msec will be provided, as necessary.

Table 6: ECG Interval Categories

Heart Rate (bpm)	Heart Rate Change from Baseline (bpm)	PR Interval (msec)	PR Percentage Change from Baseline (%)	QRS Interval (msec)	QT _c F (msec)	QT _c F change from Baseline (msec)
> 120	≥ 20	≥ 200	≥ 15	≥ 120	Males:	≤ 30
> 130	≥ 30	≥ 220	≥ 25		< 430	>30, ≤ 60
					≥ 430	> 60
					≥ 450	
					≥ 470	
					≥ 480	
					≥ 500	
					Females:	
					< 450	
					≥ 450	
					≥ 470	
					≥ 480	
					≥ 500	

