**Study Endpoints:**

The primary study endpoint is:

- Incidence and severity of treatment-emergent adverse events, changes in laboratory safety tests, ECGs, and vital sign measurements.

[figure not shown]

[figure not shown]

Additional endpoints are:

- [REDACTED]
- [REDACTED]
- [REDACTED]
- [REDACTED]
- [REDACTED]

[figure not shown]

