**Table 1: Schedule of Study Procedures**

Study Procedures	Day 1	WEEK VISITS +/- 5 Days								Early Study Drug Discontinuation l + 5 days from last dose	EOS 4 Weeks Post Last Dose l - 3 to + 5 days
		Year 1	W4	W12		W24	W36	W48	W52		
		Year 2			W60	W72	W84	W96	W104		
		Year 3			W108	W120	W132	W144	W156		
Informed Consent	X										
Review Inclusion/Exclusion Criteria	X										
Physician Global Assessment (PGA)	X		X	X	X	X	X	X	X	X	X
Pregnancy Test (females of child-bearing potential)	X		X e	X e	X e	X e	X e	X e	X e	X e	X e
FSH	X a										
											
In Clinic Dosing - Study Drug Dosing	X k										
Vital Signs (Temp, HR, BP, Respirations)	X l		X l	X l	X l	X l	X l	X l	X l	X	X
Safety Laboratory (Chemistry, Hematology)	X a, m		X	X	X	X	X	X		X	X
Physical Exam	X a		X	X	X	X	X	X	X	X	X
Smoking Status	X a								X		X
Weight	X a								X		
Medical History / Demographics	X a, b										
Concomitant Medication /Adverse Event Review	X		X	X	X	X	X	X	X	X	X
Overnight Fasting Lipid Panel			X	X	X	X	X	X		X	X
											
											
											
12-Lead Electrocardiogram (ECG)	X a			X				X	X		
Study Drug Dispensing	X		X	X	X	X	X	X	X e		
Study Drug Accountability			X	X	X	X	X	X	X	X	
Subject eDiary Daily Compliance Review			X h	X h							
Subject Symptom Recall and Compliance Review					X i	X i	X i	X i	X i	X i	
Dispense Subject eDiary	X h										
Return of Subject eDiary				X h							

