### **6.3.5. Early Study Drug Discontinuation**

Subjects who prematurely discontinue the Study drug prior to 3 years completion due to AEs, loss of response, lack of efficacy or any other reason besides withdrawal of consent during the LTS Study will be asked to return for an Early Study Drug Discontinuation visit. This visit will be conducted within 5 days after the last dose of Study drug.

Subjects should be instructed to fast from food and non-clear liquids on the evening prior to the visit to ensure a minimum 8-hour fast prior to the fasted blood sample collection.

Subjects will also return for the End of Study visit for collection of safety data and assessment of disease activity.

The Schedule of Study Procedures is summarized in [Table 1](#).

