#### **6.4.1.7. 12-Lead Electrocardiograms**

Interpretable ECG recordings (e.g., without artifacts) will be obtained according to the Schedule of Study Procedures (Table 1). Twelve-lead safety ECGs will be collected in singlet at each scheduled time point.

ECGs must be performed after the subject has been resting in a supine position for at least 10 minutes.

For monitoring purposes, the investigator must review, provide interpretation for ECG recordings other than sinus rhythm on the ECG tracing, sign, and date all safety ECG tracings. Paper copies of ECG tracings will be kept as part of the subject's Study file at the site.

If at a particular post dose time point, the QTcF is > 500 msec and/or 60 msec longer than the value at Day 1 or the mean QRS interval is > 130 msec, a decision on Study drug discontinuation should be made by the investigator with input from the Study Medical Monitor, if feasible. The investigator should also consider evaluating the subject for potential concurrent risk factors (e.g., electrolyte abnormalities, concomitant medications known to prolong the QT interval, severe bradycardia).

Results from a plasma TD-1473 exposure QTc analysis of data obtained from the SAD and MAD Study in healthy subjects and preclinical data were used in considering frequency and replicate ECGs required for this Study.

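### No ECG is scheduled at the Early Study Drug Discontinuation or EOS visit, so the ECG tables describe subjects who stayed on drug to an ECG week; the SAP should summarise the last on-treatment and worst post-baseline ECG.

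*SAP*

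**What the plan says.** - **Endpoint.** The protocol synopsis gives the primary endpoint as "Incidence and severity of treatment-emergent adverse events, changes in laboratory safety tests, ECGs, and vital sign measurements". SAP 1 rules out inferential tests, so this is a descriptive endpoint with ECG as one component.
- **Schedule.** Protocol Table 1 and SAP Table 4 carry the same ECG row: marks at Day 1, W12, W48/96/144 and W52/104/156, and empty cells at Early Study Drug Discontinuation and EOS. Vital signs, safety laboratory tests, fasting lipids and physical examination are marked at both of those visits.
- **Text around the schedule.** Protocol 6.4.1.7 states that "Twelve-lead safety ECGs will be collected in singlet at each scheduled time point". Sections 6.3.5 and 6.3.6 refer back to Table 1 for the two exit visits, and 6.6.1 asks only for the tests listed for the discontinuation visit. Section 6.1 allows extra ECGs when clinically indicated.
- **Who attends the discontinuation visit.** Protocol 6.3.5 covers "Subjects who prematurely discontinue the Study drug prior to 3 years completion due to AEs, loss of response, lack of efficacy or any other reason" other than withdrawal of consent, and says that "This visit will be conducted within 5 days after the last dose of Study drug".
- **Analysis.** SAP 3.4.3.3 says that "changes from baseline values at each assessment time point to the end of study will be presented by treatment group" and gives the categorical table by visit and time point. It adds that "Subjects without a postbaseline measurement for a given treatment period will be excluded from the summary statistics", applied time point by time point. SAP 3.1 restricts summaries to scheduled or windowed visits unless noted otherwise, and sends unscheduled data to listings. SAP 3.4.3.3 notes no exception for its tables.

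**The concern.** The discontinuation visit takes place close to last dose and collects every other main safety measure. Without an ECG there, whether a subject appears in the ECG tables, and for how much exposure, depends on staying on drug until an ECG week. Staying on drug is not independent of safety, because adverse events are among the reasons for stopping.

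Early termination makes this more important. SAP 1 reports that the study was stopped because of lack of efficacy in Study 0157, and Protocol 6.6.1 lists sponsor termination among the reasons for leaving. A route planned for a subset became the exit for everyone still on drug before Week 156. A reader who sees change-from-baseline tables by visit cannot tell how much of the exposure they cover.

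**Working it through.** The plan has no power or precision figure to reproduce. The 500 subjects are an anticipated rollover count, and the analysis is descriptive.

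**1. Place the ECG marks.** In Protocol Table 1 the header, year, PGA, laboratory and ECG rows each split into 12 fields, so each mark can be assigned to a column. The ECG marks fall at weeks 0, 12, 48, 52, 96, 104, 144 and 156. SAP Table 4 shows the same pattern.

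**2. Gaps between scheduled ECGs** (later week minus earlier week):

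| Interval | Gap (weeks) |
|---|---|
| Day 1 to W12 | 12 − 0 = 12 |
| W12 to W48 | 48 − 12 = 36 |
| W48 to W52 | 52 − 48 = 4 |
| W52 to W96 | 96 − 52 = 44 |
| W96 to W104 | 104 − 96 = 8 |
| W104 to W144 | 144 − 104 = 40 |
| W144 to W156 | 156 − 144 = 12 |

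Ignoring visit windows, a subject who stops just before the next ECG visit has a last scheduled ECG that is older than last dose by nearly the whole gap. Before W12, the only scheduled ECG is the baseline.

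**3. Follow two subjects through the rules.**
- Stops at Week 10: has a baseline ECG and no scheduled post-baseline ECG, and so no data in the change-from-baseline or categorical tables. Any clinically indicated ECG is listed.
- Stops at Week 46: is in the W12 tables and nowhere later. The last scheduled ECG is 46 − 12 = 34 weeks before stopping.

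**4. Scale, for illustration only.** The documents give no discontinuation rate and no final enrolment. Assume a constant hazard with a proportion *d* stopping by Week 52, and apply it to the planned 500:

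- stop before W12: 500 × [1 − (1 − *d*)^(12/52)]
- stop between W12 and W48: 500 × [(1 − *d*)^(12/52) − (1 − *d*)^(48/52)]

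| Assumed *d* | No scheduled post-baseline ECG | Only the W12 ECG |
|---|---|---|
| 10% | 12 | 34 |
| 20% | 25 | 68 |
| 40% | 56 | 132 |
| 60% | 95 | 190 |

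A constant hazard does not describe a sponsor termination on a calendar date. The table shows the order of size and does not estimate what happened.

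**The case against.** **The ECG frequency was a reasoned choice.** Protocol 6.4.1.7 says that an exposure–QTc analysis and preclinical data informed ECG frequency and replication, and Protocol 1.5 reports no adverse ECG changes relative to placebo in Phase 1b. This stands as support for sparse sampling. It does not tell the reader of the tables how much exposure they cover.

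**Much of the information is already there.** The 8-point summary gives *n* at each visit. All ECGs are listed, as are last-dose dates, and QTcF above 500 msec or an increase above 60 msec gets its own listing where needed. Clinically significant ECG abnormalities are recorded as adverse events. This stands too, and it is why early stoppers cannot be said to contribute nothing. But *n* by visit does not give the number with no post-baseline ECG at any visit, and the interval from last ECG to last dose would have to be worked out subject by subject.

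**The phrase about the end of study is not a contradiction.** A reader might take "changes from baseline values at each assessment time point to the end of study will be presented by treatment group" as promising an ECG at EOS that the schedule omits. It does not: it refers to the assessment time points that exist, up to study end. The vital-signs text in SAP 3.4.3.2, where an EOS assessment is scheduled, names the end of study separately. The evidence for this point is the schedule.

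**An exit ECG may not be fully on drug.** Protocol 1.5 equates 7 days with about 5 half-lives, so 5 days is 5 × 5/7 ≈ 3.6 half-lives, leaving about 2^(−3.6) ≈ 8% of drug. This stands, and means that any on-treatment ECG summary needs a stated window.

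**Conduct is over.** SAP 1 puts all last doses by 09SEP2021 and end-of-study visits by 11OCT2021. A schedule change cannot help this study, so only analysis and reporting remain open.

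**Conclusion.** The point holds as a limit on coverage and selection in the ECG tables. Subjects who stopped before W12 have no scheduled post-baseline ECG. For those who stopped between ECG visits, the last scheduled ECG may precede last dose by up to about 36 weeks (W12–W48), 44 weeks (W52–W96) or 40 weeks (W104–W144). Subjects whose last dose falls at an ECG visit, including those who complete W156, are not affected.

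A reader might go further and infer that the ECG results are biased towards safety. The documents do not support that: they give neither the number affected nor any ECG finding among early stoppers, so the direction and size of any distortion are unknown.

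The conclusion assumes that the machine-read columns are placed correctly, which the two agreeing tables and equal field counts support. It also assumes that SAP 3.1 keeps unscheduled ECGs out of the tables. Since SAP 3.1.3 uses the visit named on the CRF, an ECG taken for cause and recorded under an exit visit might be tabulated; the SAP does not say.

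**What to change.** **In SAP 3.4.3.3**, by dose:

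1. Add a last on-treatment ECG summary (value and change from baseline), with on-treatment defined as a stated number of days from last dose.
2. Add a worst post-baseline ECG summary using the Table 6 categories.
3. Include unscheduled ECGs in both, as a stated exception to SAP 3.1.
4. Report the number of subjects with no post-baseline ECG, and a descriptive summary of time from last ECG to last dose.

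**In the CSR**, state that the ECG conclusion extends only to the last on-treatment ECG.

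**Cost.** A few table rows, all from data already collected. Unscheduled ECGs are taken for cause, so the worst-value summary will tend to look less favourable than routine sampling would and should be labelled accordingly.

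**The schedule.** It may be tempting to offset an exit ECG by dropping those at W48/W96/W144. That is not recommended: ECG weeks would become 0, 12, 52, 104 and 156, and the gaps after W12 would be 40, 52 and 52 weeks, against a present maximum of 44. Nor would it clearly be free of added procedures, since a subject who stops before W48 gains an ECG and saves none. An ECG in the Early Study Drug Discontinuation column is worth considering only if this schedule is reused, at a cost of one ECG per early discontinuer.

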## **6. STUDY PROCEDURES**

### **6.1. Schedule of Study Procedures**

Study procedures will be performed only after written informed consent is obtained. A subject is considered to be enrolled once the informed consent has been signed.

The Schedule of Study Procedures is summarized in [Table 1](#).

Additional safety tests, such as vital signs (BP, heart rate, respiratory rate, and body temperature), physical exams, ECGs, and laboratory safety tests, may be obtained during the course of the study as clinically indicated to ensure appropriate safety monitoring.

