3. STATISTICAL ANALYSES

3.1. General Considerations

All individual data will be listed as measured. All statistical summaries and analyses will be performed using SAS software (SAS Institute, Cary, North Carolina, USA).

All data from scheduled and unscheduled visits will be presented in the subject listings. However, unless noted otherwise, only data from scheduled/windowed visits will be included in the summaries, statistical analysis, and calculation of derived parameters.

Summary tables and listings (e.g., post text tables and individual subject data listings are prepared according to ICH Guideline E3) include a “footer” providing explanatory notes.

Continuous data will be summarized using an 8-point descriptive summary (n, mean, standard deviation, median, interquartile range [25% quartile, 75% quartile]), minimum, and maximum) unless otherwise specified.

Categorical data will be summarized using counts and percentages. Percentages will be shown to 1 decimal place and percentages for zero counts will be omitted.

For safety assessments, summary statistics will be reported by treatment.

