3.1.3. Visit Windows

The visit indicated on the CRF will be used in summaries of the data.

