3.1.4. Multiple Assessments

In general, if multiple, valid, non-missing observations exist at a visit or collection time point then records will be chosen based on the following:

- The record closest to the nominal time point in question.

If 2 records are equidistant:

- The later record of the two visits.

If 2 records with same date/time

- Average (generally applies to assessments done in triplicate).

There is a special rule for laboratory test results: if there are multiple valid records within the visit window for the same visit or time point, the record(s) with the latest collection time will be selected rather than the record(s) with collection time closest to the nominal time. The protocol states that:

Additional and repeat laboratory safety testing for the evaluation of abnormal results and/or adverse events during the Study may be performed at the discretion of the investigator or upon request of the Sponsor.

Hence, the latest laboratory test result associated with a visit or time point will be selected for summarization. All results will be provided in listings.

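### SAP Table 6 counts ECG threshold values at scheduled visits only, so a value seen only on an unscheduled ECG, such as QRS above 130 msec, enters no ECG count

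*SAP*

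**What the plan says.** **Which records enter a summary.** SAP 3.1 sends unscheduled data to the subject listings. Unless noted otherwise, "only data from scheduled/windowed visits will be included in the summaries, statistical analysis, and calculation of derived parameters". SAP 3.1.3 settles where a record belongs: "The visit indicated on the CRF will be used in summaries of the data".

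**Which record is used when a visit has several.** SAP 3.1.4 takes the one closest to the nominal time. For a tie it takes "The later record of the two visits". Records with the same date and time are averaged. The rule that always takes the latest record is for laboratory tests only.

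**How ECGs are reported.** Under SAP 3.4.3.3, the counts of subjects with ECG values and changes "in the ranges shown in Table 6 will be presented in Electrocardiogram Categorical Summary by Visit and Time Point". The normal/borderline/prolonged QTcF groups go in the same summary. The section adds two kinds of listing: "All recorded values for the standard 12 lead electrocardiogram parameters will be presented in a by-subject listing", and "A separate listing of subjects with values of QTcF > 500 msec or an increase > 60 msec will be provided".

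**What the protocol allows.** Section 6.1 provides that "physical exams, ECGs, and laboratory safety tests, may be obtained during the course of the study as clinically indicated". Section 6.4.1.7 says "Twelve-lead safety ECGs will be collected in singlet at each scheduled time point". The same section asks for a decision on stopping study drug if QTcF exceeds 500 msec, if QTcF is 60 msec longer than on Day 1, or if mean QRS exceeds 130 msec.

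**The concern.** The protocol's primary endpoint includes changes in ECGs. An extra ECG is taken because something clinical prompted it, so it is more likely than a routine one to show an abnormality. The SAP nevertheless leaves exactly these recordings out of its ECG counts.

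The ECG table could therefore show no subject at QRS of 120 msec or more when a subject had 134 msec on an unscheduled tracing. Suppose that finding was asymptomatic, was judged not clinically significant, and did not lead to stopping the drug. It would then appear in no summary table and no separate listing, only among all values in the general by-subject listing. QRS > 130 msec is the one stopping-decision trigger in protocol 6.4.1.7 that the SAP's extreme-value listing leaves out.

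**Working it through.** There is no sample-size or test figure to reproduce. The check follows a value through the rules.

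**1. Path of an ECG labelled unscheduled**
- SAP 3.1.3: the CRF label decides, so the record is not moved into a scheduled visit.
- SAP 3.1: it is excluded from summaries unless an exception is noted.
- SAP 3.4.3.3: no exception, and no any-time or worst-value row.
- Result: it adds 0 to every Table 6 count and appears in the by-subject listing.

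**2. How much the scheduled ECGs cover**

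Read by column position, the schedule of procedures has post-baseline ECGs at Weeks 12, 48, 52, 96, 104, 144 and 156. That is 7 of the 16 post-baseline week visits. The longest planned gap is 96 − 52 = 44 weeks. The Early Study Drug Discontinuation and EOS columns show no ECG. An ECG prompted by a clinical event between these visits would be an extra one.

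**3. Case A: abnormal value only on an unscheduled ECG** (illustrative values)
- Scheduled QRS: 112 and 114 msec. Unscheduled: 134 msec.
- By-visit count at ≥ 120 msec: neither scheduled value reaches it, so 0.
- Any-post-baseline count: the maximum of 112, 114 and 134 is 134, so 1 at ≥ 120 and 1 at > 130.

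**4. Case B: scheduled 134 msec, same-day repeat 118 msec** (illustrative values)

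| How the repeat is recorded | Value used | Counted at ≥ 120 | Above 130 |
|---|---|---|---|
| Labelled unscheduled | 134 | yes | yes |
| Same CRF visit, later record selected | 118 | no | no |
| Same visit, same date and time | (134 + 118)/2 = 126 | yes | no |

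This second loss is conditional. It needs both readings under one scheduled visit and the repeat selected under SAP 3.1.4. An any-post-baseline row on all records counts the 134 in all three situations.

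**5. What the separate listing covers**

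Table 6 has 7 columns. The listing addresses two: QTcF and QTcF change. The other five are heart rate (2 categories), heart rate change (2), PR (2), PR percentage change (2) and QRS (1), giving 2 + 2 + 2 + 2 + 1 = 9 categories with no extreme-value listing. By contrast, SAP 3.4.3.2 flags marked vital-sign abnormalities in their listing, and SAP 3.4.3.1 lists all abnormal laboratory values.

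**The case against.** **The SAP follows the protocol.** Protocol 8.6.5 also summarises ECGs by time point, its Table 4 has the same single QRS category (≥ 120 msec), and its examples for the extreme-value listing are QTcF only. This stands: it is a gap in the planned analysis and not a conflict between the documents.

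**No value is lost.** Every ECG is listed, the report is a synoptic CSR, and no inferential test depends on the counts. That is true, but a full listing is not a count and does not correct a zero in the ECG table.

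**Other routes exist.** Under protocol 7.2 a symptomatic or clinically significant ECG finding is recorded as an adverse event. If the drug is stopped, SAP 3.2.2 counts the discontinuation by reason. These routes narrow what goes unreported to values that the investigator saw and judged benign. They feed adverse event and disposition tables, so the ECG count stays wrong.

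**The same-day repeat case is weak.** It does depend on CRF labelling and record selection, and only one of its three branches loses the value from the ≥ 120 count. The main point does not rely on it.

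**QRS > 130 msec is a rule for managing individual subjects.** It is also worded as a mean, which is undefined for single tracings. Both remarks are fair. It is still the one trigger in its set that the listing omits, and protocol 8.6.5 leaves the listing criteria to the SAP.

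**The table specifications are a separate document.** SAP section 1 says so, and they might contain such a row. The SAP's own text excludes unscheduled data by default and states no ECG exception.

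**Conclusion.** The concern holds. As the SAP is written, a threshold value found only on an ECG labelled unscheduled contributes 0 to every ECG count, so part of the primary safety endpoint can be under-counted in its own table. Each affected subject is missing from every category that the value reaches; in Case A the count is 0 instead of 1.

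The number of such subjects cannot be stated, because the documents give no figure for unscheduled or repeat ECGs. The QRS values above are illustrations. The conclusion assumes that extra ECGs carry an unscheduled CRF label and that the unseen table specifications add no exception; an extra ECG entered under a scheduled visit could be counted if SAP 3.1.4 selects it. The change should be made, but it affects reporting completeness and no formal inference.

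**What to change.** In SAP 3.4.3.3:

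1. Add an any-post-baseline-value row to the Table 6 summary, using all post-dose ECGs, whether scheduled, repeat or unscheduled.
2. State that the visit restriction in SAP 3.1 and the record selection in SAP 3.1.4 do not apply to that row.
3. Add a QRS > 130 msec category to the row.
4. Add QRS > 130 msec to the criteria for the separate extreme-value listing.

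The cost is one sentence of SAP text, one summary row with one added category, and one listing condition. No new data are needed because the ECGs are already collected and listed. No protocol change is needed because protocol 8.6.5 leaves the extreme-value criteria to the SAP.

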**Table 4: Thresholds for ECG**

Heart Rate (bpm)	Heart Rate Change from Baseline (bpm)	PR Interval (msec)	PR Percent Change From Baseline (%)	QRS Interval (msec)	QTcF (msec)	QTcF change from Baseline (msec)
> 120	≥ 20	≥ 200	≥ 15	≥ 120	Males:	≤ 30
> 130	≥ 30	≥ 220	≥ 25		≤ 430	> 30, ≤ 60
		Optional:			≥ 430	> 60
		≥ 240			≥ 450	
		≥ 260			≥ 470	
		≥ 280			≥ 480	
		≥ 300			≥ 500	
					Females:	
					≤ 450	
					≥ 450	
					≥ 470	
					≥ 480	
					≥ 500	

A listing of subjects with extreme values or changes, as specified in the SAP (e.g., values of QTcF > 500 msec, QTcF increases from baseline > 60 msec) will be provided.

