1. INTRODUCTION

This statistical analysis plan (SAP) outlines the planned summarization and analysis of clinical data collected in the long-term safety (LTS) study of Protocol 0164 for TD-1473. Specifications for tables, figures, and data listings are contained in a separate document.

The results of the planned analyses will be presented in a synoptic clinical study report (CSR) which will include analyses of study subject data and safety endpoints. Inferential statistical tests will not be performed. The protocol-planned efficacy analyses will be excluded as they are not necessary for a synoptic CSR.

The 0164 study was terminated early due to lack of efficacy in the 0157 study, for all subjects the date of last dose occurred by 09SEP2021 and the end of study visit by 11OCT2021.

The analysis of pharmacokinetics data (derivation and summarization of individual PK parameters) is outside the scope of this document and is not addressed here.

This document describes the a priori plan for analysis. Any substantive modification to this analysis plan will be identified in the CSR.

Information in the appendices to the SAP are not considered a formal section of the signed SAP.

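### In SAP 3.4.3.3 the male Normal/Borderline/Prolonged QTcF scheme leaves a value of exactly 430 msec unclassified

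*SAP*

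**What the plan says.** SAP 3.4.3.3 plans a by-visit categorical ECG summary built on Table 6. It adds that "in the same summary, QTcF will also be summarized by the following categories", and defines three levels by sex:

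- The first is "Normal (males < 430 , females ≤ 450", so the male limit is strict and the female limit is inclusive.
- The second, Borderline, covers males above 430 up to and including 450, and females above 450 up to and including 470.
- The third is "Prolonged (males > 450 , females > 470".

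Table 6, in the same section, splits males at < 430 and ≥ 430 and females at < 450 and ≥ 450. Further rows at higher thresholds are cumulative. Protocol Table 4 lists the lowest male pair as ≤ 430 and ≥ 430, and the lowest female pair as ≤ 450 and ≥ 450.

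The same SAP section removes subjects without a postbaseline measurement from the denominator at a time point. It lists all recorded ECG values and separately lists QTcF above 500 msec or increases above 60 msec. SAP section 1 states that "Inferential statistical tests will not be performed".

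**The concern.** The three levels read as a partition: each subject with a QTcF value should fall in exactly one. For males they do not form one, because the first level stops short of 430 and the second begins beyond it. Neither document assigns the value 430 anywhere else.

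ECG change is part of the primary endpoint in the protocol synopsis, and SAP 3.3 sends the primary objective to the safety analyses in 3.4. This is therefore an operative rule for a primary safety output. Applied literally, it keeps a male at 430 in the denominator, since he has a measurement, and puts him in no numerator. The three percentages would then not total 100, and a programmer would have to drop the value or choose a side without instruction.

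**Working it through.** The plan states no figure to reproduce. The check is whether each rule, as printed, puts every QTcF value in exactly one level.

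**Inputs.** The three-level rules and Table 6 come from SAP 3.4.3.3. The comparison rows come from protocol Table 4.

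**Step 1: males at the boundaries (msec).**

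| Value | Normal (< 430) | Borderline (> 430 and ≤ 450) | Prolonged (> 450) | Levels met |
|---|---|---|---|---|
| 429 | yes | no | no | 1 |
| 430 | no | no | no | 0 |
| 431 | no | yes | no | 1 |
| 450 | no | yes | no | 1 |
| 451 | no | no | yes | 1 |

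Testing every whole value from 300 to 600 msec gives one failure, at 430, which meets no level.

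**Step 2: females.** Normal ≤ 450, Borderline > 450 to ≤ 470 and Prolonged > 470 meet edge to edge. Over the same range there are no gaps and no overlaps.

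**Step 3: SAP Table 6.** The pairs < 430 / ≥ 430 (males) and < 450 / ≥ 450 (females) have no gap or overlap. A male 430 is counted in ≥ 430.

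**Step 4: protocol Table 4.** Its lowest pairs overlap, so a male 430 and a female 450 each meet both rows. SAP Table 6 replaces these pairs with the complementary ones in step 3.

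**Step 5: effect on the counts.** Let n be the subjects with a value at a visit in a treatment group, and k the males among them at exactly 430. Then

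Normal + Borderline + Prolonged = n − k,

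and the percentages total 100 × (n − k)/n. The documents do not allow k to be calculated.

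**Step 6: possible repairs.**

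- Male Normal ≤ 430, followed by > 430 to ≤ 450 and > 450: every whole value from 300 to 600 falls in exactly one level.
- Male Normal < 430, followed by ≥ 430 to ≤ 450 and > 450: each level begins where the one before ends, so this is also complete.

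**Step 7: illustration of frequency, on assumptions only.** Suppose QTcF is rounded to whole msec and male values are normal with mean 400 to 415 and SD 18 to 20 msec. None of this is in the documents. The share recorded as 430 is P(429.5 < X < 430.5), close to the normal density at 430:

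- mean 400, SD 18: 0.55%
- mean 415, SD 18: 1.57%

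The other corners of that range lie between these two figures.

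**The case against.** The strongest reply is that the gap may never matter in practice. The SAP says QTcF is calculated by the Fridericia correction, which generally does not give a whole number, and it has no rounding rule for ECG values. Classified unrounded, an exact 430 would be very rare. The study also stopped early (SAP section 1), the number of treated males is not given, and ECGs are scheduled at only a few visits. Zero affected readings is plausible even with rounding. This stands: the documents support saying that a 430 can occur, not that it will.

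It is also fair to say that little is lost. A male at 430 still appears in Table 6, in the descriptive statistics and in the listing. That stands too.

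The sentence is irregularly printed, so a lost inclusive sign in the text as read cannot be wholly excluded. It is unlikely, because the female inclusive sign survives in the same bracket and Table 6 also prints < 430 for males.

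Some wider readings are tempting but not supported:

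- **That the categorical ECG counts in general fail to add up.** Table 6 places 430, and its upper rows are cumulative and not meant to sum.
- **That 450 is handled wrongly because the text puts a male 450 in Borderline while Table 6 counts it in ≥ 450.** These are two displays, each defined at that value. The difference is one of convention.
- **That protocol Table 4 leaves a live double count.** SAP Table 6 has already replaced those rows.
- **That the male strict sign must be the slip.** The female rule suggests so, but Table 6 prints the same < 430, so the Borderline limit could equally be the slip.

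**Conclusion.** The point holds as a one-value gap, for males only, at exactly 430 msec, in the three-level scheme only. That the definition is incomplete follows from the printed rule and needs no assumption. That counts fall short in practice requires rounding to whole msec, or an exact 430 arising some other way, and the documents settle neither.

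Where it occurs, the shortfall is one subject per male reading of 430 at a visit. The percentages in step 7 of the working only illustrate the scale and are not an estimate for this trial. The consequence is minor: a descriptive table that may not total, with no effect on any test or on the listing of extreme QTcF values. It is worth correcting because the rule is wrong as written and the correction is almost free.

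**What to change.** Change one symbol in the SAP 3.4.3.3 text, in one of two ways:

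- make male Normal ≤ 430, parallel to the female ≤ 450; or
- make male Borderline ≥ 430 to ≤ 450, which matches the Table 6 split at < 430 / ≥ 430.

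Both close the gap, and the sponsor need only choose one. Table 6 can stay as it is. A short statement of whether QTcF is rounded before classification would remove the remaining ambiguity. The cost is the symbol edit, that optional sentence and the matching line of programming. No new data or analysis is needed.
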